4.3.7 Neurological irAEs

Rule out non-inflammatory causes. If a non-inflammatory cause is identified, treat accordingly and continue therapy per protocol (Table 9).

Table 9: Neurological irAE Management Algorithm

	Neurological irAEs										
CTCAE Grade of Neurological Toxicity	Management	Follow-Up									
Grade 1 Asymptomatic or mild symptoms; intervention not indicated.	Continue AGEN1884 therapy per protocol.	 Continue to monitor subject. If worsens: Treat as grade 2 or grade 3-4. 									
Grade 2 Moderate symptoms; limiting instrumental ADL.	 Delay AGEN1884 therapy per protocol. Treat symptoms per local guidelines. Consider 0.5-1.0 mg/kg/day methylprednisolone IV or oral equivalent. 	 If returns to baseline: Resume AGEN1884 therapy per protocol. If worsens: Treat as grade 3-4. 									
Grade 3-4 Severe symptoms; limiting self-care ADL; life-threatening.	 Discontinue AGEN1884 therapy per protocol. Obtain neurology consult. Treat symptoms per local guidelines. 1.0-2.0 mg/kg/day methylprednisolone IV or IV equivalent. Add prophylactic antibiotics for opportunistic infections. 	 If improves to grade 2: Taper corticosteroids over ≥1 month. If worsens or atypical presentation: Consider IV immunoglobulin or other immunosuppressive therapies per local guidelines. 									

ADL: activities of daily living; CTCAE: Common Terminology Criteria for Adverse Events; irAE: immune-related adverse event; IV: intravenous; kg: kilogram; mg: milligram.

4.4 Adverse Drug Reactions Requiring Treatment Discontinuation or Modifications

An ADR is defined as all noxious and unintended responses to a medicinal product, related to any dose. A causal relationship between the medicinal product and an AE is deemed at least a reasonable possibility if the relationship cannot be ruled out by another cause.

4.4.1 Dose Reductions

No dose reductions are allowed. Each subject will stay on the regimen dose levels assigned in the trial unless treatment needs to be stopped. Dose reductions or dose escalations of AGEN1884 are not permitted.

Confidential Page 45 of 78

4.4.2 Permanent Treatment Discontinuation

The following ADRs require permanent treatment discontinuation of AGEN1884:

Any grade 4 ADRs except for single laboratory values out of normal range that are unlikely related to trial treatment as assessed by the investigator, do not have any clinical correlate, and resolve within 7 days with adequate medical management.

Any grade 3 ADRs except for any of the following:

- Transient (≤6 hours) grade 3 flu-like symptoms or fever, which are controlled with medical management.
- Transient (≤24 hours) grade 3 fatigue, local reactions, headache, nausea, or emesis that resolves to grade ≤1.
- Single laboratory values out of normal range (excluding grade ≤3 liver function test increase) that are unlikely related to trial treatment according to the investigator; do not have any clinical correlate; and resolve to grade ≤1 within 7 days with adequate medical management.
- Tumor flare phenomenon, defined as local pain, irritation, or rash localized at sites of known or suspected tumor.
- Any grade ≥3 drug-related amylase or lipase abnormality that is not associated with symptoms, or clinical manifestations of pancreatitis does not require dose delay. The trial medical monitor should be consulted for such grade ≥3 amylase or lipase abnormalities.
- Increases in ECOG performance status to ≥3 that do not resolve to ≤2 by Day 14 of the following cycle (infusions should not be given on the following cycle if ECOG performance status is ≥3 on day of study drug administration).

Any grade 2 ADR should be managed as follows:

- If a grade 2 ADR resolves to grade ≤1 by the last day of the current cycle, trial treatment may continue.
- If a grade 2 ADR does not resolve to grade ≤1 by the last day of the current cycle, infusions should not be administered during the following cycle. If, at the end of the following cycle, the event has not resolved to grade 1, the subject should permanently discontinue treatment with AGEN1884.
- For grade 2 ADRs related to hormone insufficiencies that can be managed by replacement therapy, up to 2 subsequent doses may be omitted.
- Upon the second occurrence of the same grade 2 ADR (except for hormone insufficiencies that can be managed by replacement therapy) in the same subject, treatment with AGEN1884 should be permanently discontinued.

Confidential Page 46 of 78

Subjects who received systemic corticosteroids for management of any drug-related toxicity must be off corticosteroids or have tapered down to an equivalent dose of prednisone ≤ 10 mg/day for study treatment to be resumed.

All infusion-related and hypersensitivity reactions (grades 1-4) should be handled according to the guidelines in Table 2.

Subjects in Phase 2 with HCC will be discontinued for any of the following reasons:

- New onset clinical ascites
- Upper gastrointestinal bleeding due to portal hypertension
- Encephalopathy
- Coagulopathy secondary to liver disease
- Worsening Child-Pugh score to 9
- ALT, AST elevations \geq 20 x ULN

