4.3 Management of Immune-Related Adverse Events

Immuno-oncology agents such as AGEN1884 are associated with immune-related adverse events (irAEs). Early recognition and management of irAEs may mitigate severe toxicity. Investigators should also monitor subjects closely for potential irAEs, which may manifest after weeks of treatment, at the earliest. Such events may consist of persistent rash, diarrhea, colitis, autoimmune hepatitis, pneumonitis, encephalitis, arthritis, glomerulonephritis, cardiomyopathy, or uveitis and other inflammatory eye conditions.

Management algorithms have been developed to assist investigators in assessing and managing the following groups of irAEs: gastrointestinal, pulmonary, dermatological, renal, hepatic, neurological, and endocrine, among others.

Adverse events (both non-serious and serious) associated with drug exposure and consistent with an immune phenomenon may represent an immunologic etiology. These irAEs may be predicted based on the nature of the study drugs, their mechanism of action, and reported experience with immunotherapies that have a similar mechanism of action. An irAE can occur shortly after the first dose or several months after the last dose of treatment. Particular attention should be paid to AEs that may be suggestive of potential irAEs, as outlined below.

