4.3.1 Dermatological irAEs

Rule out non-inflammatory causes. If a non-inflammatory cause is identified, treat accordingly and continue therapy per protocol (Table 3).

Confidential Page 37 of 78

Table 3: Dermatological irAE Management Algorithm

	Dermatological irAEs	
CTCAE Grade of Rash	Management	Follow-Up
Grade 1-2 Covering ≤30% body surface area	 Symptomatic therapy (e.g., antihistamines, topical corticosteroids). Continue AGEN1884 therapy per protocol. 	 If persists >1 to 2 weeks or recurs: Consider skin biopsy. Delay AGEN1884 therapy. Consider 0.5-1 mg/kg/day methylprednisolone IV or oral equivalent. Once improving, taper corticosteroids over ≥1 month; consider prophylactic antibiotics for opportunistic infections; and resume AGEN1884 therapy per protocol. If worsens: Treat as grade 3-4.
Grade 3-4 Covering >30% body surface area; life-threatening consequences	 Delay or discontinue AGEN1884 therapy per protocol. Consider skin biopsy. Dermatology consult 1-2 mg/kg/day methylprednisolone IV or IV equivalent. 	 If improves to grade 1: Taper corticosteroids over ≥1 month; add prophylactic antibiotics for opportunistic infections. Resume AGEN1884 therapy per protocol.

CTCAE: Common Terminology Criteria for Adverse Events; irAE: immune-related adverse event; IV: intravenous; kg: kilogram; mg: milligram

Confidential Page 38 of 78

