4.3.2 Gastrointestinal irAEs

Rule out non-inflammatory causes. If non-inflammatory cause is identified, treat accordingly and continue therapy. Opiates/narcotics may mask symptoms of perforation. Infliximab should not be used in cases of perforation or sepsis (Table 4).

Table 4: Gastrointestinal irAEs Management Algorithm

Gastrointestinal irAEs							
CTCAE Grade of Diarrhea/Colitis	Management	Follow-Up					
Grade 1 Diarrhea: <4 stools/day over baseline. Colitis: asymptomatic.	 Continue AGEN1884 therapy per protocol. Symptomatic treatment. 	 Close monitoring for worsening symptoms. Educate subject to report worsening immediately. Consider symptomatic treatment including hydration, electrolyte replacement, dietary changes (e.g., American Dietetic Association colitis diet), and loperamide. If worsens: Treat as grade 2 or 3-4. 					
Grade 2 Diarrhea: 4-6 stools per day over baseline; IV fluids indicated <24 h; not interfering with activities of daily living (ADL). Colitis: abdominal pain; blood in stool.	 Delay AGEN1884 therapy per protocol. Symptomatic treatment. 	 If improves to grade 1: Resume AGEN1884 therapy per protocol. If persists >5 to 7 days or recurs: 0.5-1 mg/kg/day methylprednisolone or equivalent. When symptoms improve to grade 1, taper corticosteroids over ≥1 month; consider prophylactic antibiotics for opportunistic infections; resume AGEN1884 therapy per protocol. If worsens or persists >3 to 5 days with oral corticosteroids: Treat as grade 3-4. 					
Grade 3-4 Diarrhea (grade 3): ≥7 stools per day over baseline; incontinence; IV fluids ≥24 h; interfering with ADL. Colitis (grade 3): severe abdominal pain, medical intervention indicated, peritoneal signs. Grade 4: life-threatening, perforation	 Discontinue AGEN1884 therapy per protocol. 1-2 mg/kg/day methylprednisolone IV or equivalent. Add prophylactic antibiotics for opportunistic infections. Consider lower endoscopy. 	 If improves: Continue corticosteroids until grade 1, then taper over ≥1 month. If persists >3 to 5 days, or recurs after improvement: Add infliximab 5 mg/kg (if no contraindication). Note: Infliximab should not be used in cases of perforation or sepsis. 					

ADL: activities of daily living; CTCAE: Common Terminology Criteria for Adverse Events; h: hour; irAE: immune-related adverse event; IV: intravenous; kg: kilogram; mg: milligram.

Confidential Page 39 of 78

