4.3.4 Hepatic irAEs

Rule out non-inflammatory causes (e.g., alcohol use, acute viral hepatitis, flare up from chronic hepatitis, co-infection [e.g., with hepatitis D], etc.). If a non-inflammatory cause is identified, treat accordingly and continue therapy per protocol. Consider imaging for obstruction and a hepatologist consult (Table 6).

Table 6: Hepatic ir AE Management Algorithm

	Hepatic irAEs										
CTCAE Grade of Liver Test Elevation	Management	Follow-Up									
Grade 1 AST or ALT >ULN to 3 x ULN and/or total bilirubin >ULN to 1.5 x ULN.	Continue AGEN1884 therapy per protocol.	 Continue liver function tests (LFT) monitoring per protocol. If worsens: Treat as grade 2 or grade 3-4. 									
Grade 2 AST or ALT >3 to ≤5 x ULN and/or total bilirubin >1.5 to ≤3 x ULN. If subject has concurrent AST or ALT >3 x ULN and total bilirubin >2 x ULN, discontinue AGEN1884 therapy per protocol (Hy's Law)	 Delay AGEN1884 therapy per protocol. Increase frequency of monitoring to every 3 days. 	If returns to baseline: Resume routine monitoring; resume AGEN1884 therapy per protocol. If elevations persist >5 to 7 days or worsen: 0.5-1 mg/kg/day methylprednisolone IV or oral equivalent. When LFT returns to grade 1 or baseline, taper corticosteroids over ≥1 month, consider prophylactic antibiotics for opportunistic infections, and resume AGEN1884 therapy per protocol.									
Grade 3-4 AST or ALT >5 x ULN and/or total bilirubin >3 x ULN.	 Permanently discontinue AGEN1884 therapy per protocol. Increase frequency of monitoring to every 1-2 days. 1-2 mg/kg/day methylprednisolone IV or oral equivalent.* Add prophylactic antibiotics for opportunistic infections. Consult gastroenterology. Consider obtaining MRI/CT scan of liver and liver biopsy if clinically warranted. 	 If returns to grade 2: Taper corticosteroids around 4 to 6 weeks. If does not improve in >3 to 5 days, worsens, or rebounds: Add mycophenolate mofetil 1 g twice daily. If no response within an additional 3-5 days, consider other immunosuppressants per local guidelines. 									

Confidential Page 41 of 78

	Hepatic irAEs	
CTCAE Grade of Liver Test Elevation	Management	Follow-Up

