4.3.6 Renal irAEs

Rule out non-inflammatory causes. If non-inflammatory cause is identified, treat accordingly and continue therapy per protocol (Table 8).

Table 8: Renal ir AE Management Algorithm

	Renal irAEs										
CTCAE Grade of Creatinine Elevation	Management	Follow-Up									
Grade 1 Creatinine >ULN and >baseline but ≤1.5 x baseline	 Continue AGEN1884 therapy per protocol. Monitor creatinine weekly. 	 If returns to baseline: Resume routine creatinine monitoring per protocol. If worsens: Treat as grade 2 or grade 3-4. 									
Grade 2-3 Creatinine >1.5 x baseline to ≤6 x ULN	 Delay AGEN1884 therapy per protocol. Monitor creatinine every 2-3 days. 0.5-1.0 mg/kg/day methylprednisolone IV or oral equivalent. Consider renal biopsy 	 If returns to grade 1: Taper corticosteroids over ≥1 month, consider prophylactic antibiotics for opportunistic infections, and resume AGEN1884 therapy and routine creatinine monitoring per protocol. If elevations persist > 7 days or worsen: Treat as grade 4. 									
Grade 4 Creatinine >6 x ULN	 Discontinue AGEN1884 therapy per protocol. Monitor creatinine daily. 1.0-2.0 mg/kg/day methylprednisolone IV or IV equivalent. Consult nephrologist. Consider renal biopsy. 	If returns to grade 1: Taper corticosteroids over ≥1 month and add prophylactic antibiotics for opportunistic infections.									

CTCAE: Common Terminology Criteria for Adverse Events; irAE: immune-related adverse event; IV: intravenous; kg: kilogram; mg: milligram; ULN: upper limit of normal.

Confidential Page 44 of 78

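### Section 4.4.2 permanently stops AGEN1884 for a grade 3 drug-related creatinine rise that Table 8 says to delay and resume; Table 3, Table 7 and Section 4.1.2 blur the same line, and no text says which rule prevails

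*Protocol*

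**What the plan says.** Protocol Section 4.4.2 lists the adverse drug reactions (ADRs) after which AGEN1884 must be stopped for good. Grade 4 ADRs are on it, apart from isolated laboratory values judged unlikely to be related. So are "Any grade 3 ADRs except for any of the following". The exceptions are brief flu-like symptoms or fever; brief fatigue, local reactions, headache, nausea or vomiting; isolated laboratory values judged unlikely to be related; tumor flare; amylase or lipase changes without symptoms; and a performance-status item. An allowance for hormone insufficiency managed by replacement appears only under the grade 2 rules.

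Other parts of the protocol handle some of the same events differently:

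- **Table 8 (Section 4.3.6).** Grades 2 and 3 of creatinine elevation share one row. Its management cell says delay. On return to grade 1 the site is to taper steroids and "resume AGEN1884 therapy and routine creatinine monitoring per protocol". Discontinuation is reached only through the grade 4 row, if the rise lasts more than 7 days or worsens.
- **Table 3 (Section 4.3.1).** The grade 3-4 rash row, defined as "Covering >30% body surface area; life-threatening consequences", says "Delay or discontinue AGEN1884 therapy per protocol". On improvement to grade 1 it says to taper steroids, "add prophylactic antibiotics for opportunistic infections. Resume AGEN1884 therapy per protocol".
- **Table 7 (Section 4.3.5).** Symptomatic endocrinopathy with an abnormal laboratory result or scan is delayed and, once improved, resumed, with no grade stated. Suspected adrenal crisis may be delayed or discontinued.
- **Section 4.1.2.** Grade 3 drug-related skin events, and grade 3 drug-related laboratory abnormalities with creatinine not excepted, are reasons to delay a dose.

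The introduction to Section 4.3 says only this about the status of the tables: "Management algorithms have been developed to assist investigators in assessing and managing the following groups of irAEs".

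**The concern.** A site that follows Table 8 exactly will re-dose a subject whom Section 4.4.2 removes from treatment permanently. A site that takes the delay option in Table 3 can do the same after rash, and the row does not exclude a life-threatening one.

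This is first a matter of subject safety. It also affects a primary result. Safety and tolerability is a primary objective of Phase 2. SAP Section 8.6.2 tabulates drug-related treatment-emergent events leading to permanent discontinuation by preferred term. For each immune-related cluster, including rash and the endocrine clusters, it also reports the percentages leading to dose hold and to discontinuation. If sites resolve the conflict differently, the same event is a hold at one site and a discontinuation at another.

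**Working it through.** No figure in the plan needs reproducing. The check is a side-by-side reading, followed by an illustrative calculation.

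**Step 1: are the table events within the scope of 4.4.2?** Section 4.4 defines an ADR by a reasonable possibility of causation. Section 5.8.6.1.2 defines an immune-related event as one associated with drug exposure. The drug-related events managed in Tables 3, 7 and 8 are therefore ADRs.

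**Step 2: are they exempt?** A drug-related creatinine rise is not, because the laboratory exception is limited to values judged unlikely to be related. Rash is named only as part of tumor flare; at most, a local reaction lasting no more than 24 hours could also qualify. A grade 3 endocrine event falls outside the hormone allowance, which sits under grade 2.

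**Step 3: compare the instructions.**

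| Drug-related event | Section 4.4.2 | Other text | Can a site satisfy both? |
|---|---|---|---|
| Grade 3 creatinine rise, back to grade 1 | Stop permanently | Table 8: delay, then resume | No |
| Grade 3 rash, back to grade 1 | Stop permanently | Table 3: delay or discontinue, with a resume line | Yes, by discontinuing |
| Grade 4 rash | Stop permanently | Table 3: same row as grade 3 | Yes, by discontinuing |
| Grade 3-4 symptomatic endocrinopathy, improved | Stop permanently | Table 7: delay, then resume; no grade limit | Only if the resume line is read as limited to grade 2 or lower |
| Grade 3 skin or laboratory event on a dosing day | Stop permanently unless exempt | Section 4.1.2: delay | Only if delay is read as a first step before stopping |

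**Step 4: is there a precedence rule?** None was found. Section 4.4.2 hands infusion and hypersensitivity reactions to Table 2 explicitly, but says nothing comparable about Tables 3, 7 or 8. The resume lines refer only to the protocol in general, which contains both 4.4.2 and 4.1.2. The note in Section 5.8.6.4, that a subject with a grade 3 or 4 event may be considered for discontinuation, is discretionary and does not settle the matter.

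**Step 5: does the pattern reveal intent?** Six irAE tables are graded: 3, 4, 5, 6, 8 and 9. Four of them stop at grade 3-4: Tables 4, 5 and 9 say "Discontinue AGEN1884 therapy per protocol", and Table 6, outside its HCC row, says "Permanently discontinue AGEN1884 therapy per protocol". Two (3 and 8) carry a resume line that reaches grade 3. Against that, 4.1.2 also treats grade 3 skin and laboratory events as grounds for delay, and ungraded Table 7 resumes. The pattern does not decide it.

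**Step 6: illustrative size.** The documents give no event rates. Assume that a share p of subjects has a grade 3 or higher drug-related rash, or a grade 3 drug-related creatinine rise, that recovers to grade 1. With n = 60 (the Phase 2 maximum in Table 1), the expected number is 60p, and the chance of at least one is 1 − (1 − p)^60.

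| Assumed p | Expected subjects | Chance of at least one |
|---|---|---|
| 1% | 60 × 0.01 = 0.6 | 1 − 0.99^60 = 45.3% |
| 3% | 60 × 0.03 = 1.8 | 1 − 0.97^60 = 83.9% |
| 5% | 60 × 0.05 = 3.0 | 1 − 0.95^60 = 95.4% |

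If every such subject resumed, the percentage discontinuing for a drug-related event would be p lower, that is 1 to 5 points; this is the assumption restated. Endocrine events under Table 7 would add to these counts.

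**The case against.** The best defense is that the tables only assist, that 4.4.2 is worded as a requirement, and that each delay or resume line is qualified by a reference to the protocol, which can be taken to include 4.4.2. On that reading a site must check 4.4.2 before resuming, and would have to override an explicit grade 4 stop to re-dose after life-threatening rash. For Table 3 this largely succeeds: the row names discontinuation as an option, so the fault there is loose drafting. A reader might infer that Table 3 orders re-dosing after life-threatening rash; it does not, although it fails to rule it out.

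The defense fails for Table 8. Its grade 2-3 management cell offers no discontinuation, and if 4.4.2 always overrode it, the resume instruction would have no application to a grade 3 drug-related rise.

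A reader might also infer from the four tables that stop at grade 3-4 that 4.4.2 is plainly the intended rule. The documents do not support that. Section 4.1.2 is protocol text rather than an assisting algorithm, and it lists the same two event types as reasons to delay. It does not say that dosing then resumes, so it is not a flat contradiction, but it leaves intent open.

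Finally, the affected SAP outputs are descriptive and the sample size is not inferential, so no test or power statement is at risk. That limits the statistical consequence but does not answer the safety one.

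**Conclusion.** The inconsistency is real and should be corrected. Table 8 directly contradicts Section 4.4.2 for a grade 3 drug-related creatinine rise. Table 3 permits what 4.4.2 forbids without requiring it. Section 4.1.2 and Table 7 leave the same boundary unclear for skin, laboratory and endocrine events. Since no text ranks these rules, the documents do not show which outcome the sponsor intends.

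The conflict rests on the wording alone. Its size does not: the 0.6 to 3.0 subjects among 60, and the 1 to 5 point shift, depend wholly on an assumed 1% to 5% rate and, for the shift, on every such subject being resumed. They show only that one or a few subjects could plausibly be affected, and should not be read as a forecast.

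**What to change.** State one precedence rule: where Section 4.4.2 requires permanent discontinuation, it overrides the delay criteria in Section 4.1.2 and the delay and resume lines in Tables 3, 7 and 8. Leave unchanged the Table 2 rule for infusion reactions and the HCC-specific hepatic rules in 4.1.2 and Table 6. Then conform the text:

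- **Table 8:** split the grade 2-3 row so that only grade 2 may resume. Align its 7-day persistence line for grade 2 with 4.4.2, which allows until the end of the following cycle before permanent discontinuation.
- **Table 3:** make grade 4 rash a mandatory stop and replace the grade 3 delay and resume wording, keeping the steroid taper. Make the escalation line in the grade 1-2 row apply only once grade 3 is reached, so that a grade 2 rash still follows the 4.4.2 grade 2 rules.
- **Section 4.1.2:** add that delay applies unless 4.4.2 requires permanent discontinuation.
- **Table 7:** limit resumption to events after which 4.4.2 allows further dosing.

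If the sponsor instead wants resumption after a recovered grade 3 rash, creatinine rise or hormone-replaced endocrinopathy, add those events to the 4.4.2 exceptions, conditional on grade 1 or less and a prednisone equivalent of at most 10 mg/day. Grade 4 rash should remain a mandatory stop.

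The cost is amendment wording and a notice to sites, with no change to sample size, visits or assessments. The drawback of the default is that some subjects with a recovered grade 3 event come off drug. If dosing is already complete, the sponsor should identify any subject re-dosed after such an event and report how the event was classified.

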5.8.6.1.3 Adverse Drug Reaction

An ADR is defined as all noxious and unintended responses to a medicinal product, related to any dose. A causal relationship between the medicinal product and an AE is at least a reasonable possibility, i.e., the relationship cannot be ruled out.

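### Section 4.4.2 exempts isolated, unlikely-related liver-test rises from the mandatory stop at grade 4 but not at grade 3

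*Protocol*

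**What the plan says.** Protocol Section 4.4.2 lists the adverse drug reactions (ADRs) that require AGEN1884 to be stopped for good.

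- **Grade 4.** The rule covers "Any grade 4 ADRs except for single laboratory values out of normal range that are unlikely related to trial treatment as assessed by the investigator". The exempt values must also meet these conditions: "do not have any clinical correlate, and resolve within 7 days with adequate medical management".
- **Grade 3.** The rule has a longer list of exceptions. The matching one is "Single laboratory values out of normal range (excluding grade ≤3 liver function test increase) that are unlikely related to trial treatment". It also requires no clinical correlate, and resolution to grade 1 or lower within 7 days.

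An ADR is defined broadly. In Section 4.4 a causal link is "deemed at least a reasonable possibility if the relationship cannot be ruled out by another cause". In Section 5.8.6.1.3 it "is at least a reasonable possibility, i.e., the relationship cannot be ruled out".

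Section 4.3.4 has a separate algorithm for hepatic immune-related events. The grade 3-4 row of Table 6 reads "Permanently discontinue AGEN1884 therapy per protocol", and the grade 2 row adds a combined criterion: "If subject has concurrent AST or ALT >3 x ULN and total bilirubin >2 x ULN, discontinue AGEN1884 therapy per protocol". The section opens with a limit on all of this: "If a non-inflammatory cause is identified, treat accordingly and continue therapy per protocol".

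**The concern.** The two exemptions describe the same kind of event and differ in how they treat liver tests. At grade 3 the drafters held liver-test rises back from the exemption, so these rises still end treatment. At grade 4 nothing holds them back. A mandatory safety rule should not relax as severity rises.

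Hepatitis is among the immune-related events that Section 5.8.6.1.2 reports for earlier anti-CTLA-4 agents, and safety is a primary objective. What is at stake is consistent handling. Two sites facing the same isolated grade 4 rise could act differently, and both could claim to follow Section 4.4.2.

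**Working it through.** The plan states no figure on this point, so the check sets the rules side by side.

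**Step 1: a test event.** Take one isolated liver-test rise that is rated unlikely related, has no clinical correlate and is back to grade 1 or lower within 7 days. It meets every shared condition of both exemptions, so only the grade varies.

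**Step 2: can it be an ADR?** Yes. Sections 4.4 and 5.8.6.1.3 ask whether the drug can be ruled out. Section 5.9 separates unlikely from unrelated and keeps the second for events that are clearly due to something else. An event rated unlikely can therefore remain an ADR, and Section 4.4.2 then applies.

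**Step 3: apply Section 4.4.2.**

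| | Grade 3 | Grade 4 |
|---|---|---|
| General rule | Permanent stop | Permanent stop |
| Exemption for single, unlikely-related laboratory values | Yes | Yes |
| Liver tests excluded from the exemption | Yes | No |
| Resolution target within 7 days | Grade 1 or lower | None stated |
| Result for the test event | **Stop required** | **Stop not required** |

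**Step 4: look for another mandatory stop at grade 4.**

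- *Table 6.* If no non-inflammatory cause is identified and the event is handled as a hepatic immune-related event, the stop applies at grades 3 and 4 alike and there is no gap. If such a cause is identified, Section 4.3.4 sends the case back to the general rules, which means Section 4.4.2. The combined criterion needs a transaminase and bilirubin raised together, so one isolated value does not meet it.
- *Section 4.1.2.* The general liver-test delay criteria require drug-related toxicity. What remains is a delay at the investigator's judgment.
- *Sections 3.5 and 5.8.6.4.* Both let the investigator stop treatment, the second after consulting the medical monitor. Neither requires it for this event.
- *HCC rules.* The HCC list in Section 4.4.2 stops Phase 2 HCC subjects at ALT or AST of 20 x ULN or more, whatever the cause. It has no bilirubin criterion. The bilirubin delay rules in Section 4.1.2 and the HCC row of Table 6 are for HCC subjects with elevated baseline liver tests. Non-HCC subjects have no equivalent of the 20 x ULN stop.

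**Step 5: who is left.** Phase 1 is complete, so this concerns Phase 2. The gap is mainly a non-HCC subject with an identified non-inflammatory cause, a drug role rated unlikely but not ruled out, no clinical correlate and resolution within 7 days. All of these must hold together.

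For context only, non-HCC subjects make up 40/60 = 67% of Phase 2 under Protocol Section 3.1 and SAP Section 3.2. Under Protocol Section 6.1 the share is (40 - 20)/40 = 50%. These are shares of subjects under the general rule. They do not measure how often the event occurs.

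**The case against.** The best defence combines two provisions. If no other cause is found, Table 6 stops treatment at both grades. If another cause is found, it will often rule out the drug; the event is then not an ADR, and Section 4.4.2 compels nothing at either grade. This stands as far as it goes and is why the gap is so small. It does not reach the case where another cause is identified but the drug cannot be excluded.

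A second defence is that values rated unlikely are never ADRs. SAP Section 8.6.2 counts them as unrelated. One might answer that both exemptions would then have no content, but that answer is weak. The dose-limiting toxicity definition in Section 3.1.2.2 contains just such a redundant exception: it covers possibly, probably or definitely related events and then excepts unlikely-related laboratory values. The case therefore rests on the ADR definition and the causality scale in Section 5.9, which do leave unlikely events inside the rule. The SAP grouping governs tables and not dosing.

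Third, the grade 3 wording is odd, since grades 1 and 2 cannot arise in a list of grade 3 reactions. The qualifier 'grade ≤3' may be a slip for 'grade ≥3', or an artefact of text extraction. That cannot be settled from the documents. Either way, the separate grade 4 sentence contains no liver exclusion.

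**Conclusion.** The inconsistency is real and minor. For the test event, Section 4.4.2 requires a stop at grade 3 and not at grade 4, and no other mandatory rule fully closes the gap for non-HCC subjects. The conclusion assumes a literal reading of the two exemptions, and that an event rated unlikely can be an ADR because the drug has not been ruled out.

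The documents give no frequency for such rises, so no effect on the discontinuation rate can be stated. Because every condition must hold at once, the number is likely to be small.

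A reader might infer that the protocol lets dosing continue through grade 4 liver toxicity in general. It does not. Grade 4 liver ADRs that are related, symptomatic or persistent fall outside the exemption and are stopped. Even for the exempt event nothing requires further dosing, and the investigator may delay or stop. A reader might also infer that half to two thirds of Phase 2 is exposed to harm, or that a safety or efficacy endpoint is compromised. The first takes a population share for an event rate. For the second, the documents show no effect on any endpoint or planned analysis.

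**What to change.** Amend Protocol Section 4.4.2 as follows.

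1. In the grade 4 exemption, add '(excluding liver function test increase)' after the reference to single laboratory values.
2. In the grade 3 exemption, delete 'grade ≤3' from the parenthesis so that the two exclusions match.
3. In the grade 4 exemption, state the grade 3 resolution target: grade 1 or lower within 7 days.
4. Add one sentence. Phase 2 HCC subjects with elevated baseline liver tests follow the HCC-specific rules in Section 4.1.2, Table 6 (HCC row) and Section 4.4.2. HCC subjects with normal baseline liver tests stay under the general rule as well as the HCC stop list.

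The sentence in item 4 should not cover all HCC subjects. The HCC delay and re-treatment rules are largely written for those with elevated baseline values, and extending them would loosen the general liver stop for the rest.

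The cost is three wording edits and one sentence, with no new data and no SAP change. The clinical downside is that a rare subject with a transient, unlikely-related grade 4 liver-test rise would have to stop, as is already required at grade 3. That matters in a population without established alternatives. A case in which another cause rules out the drug is not an ADR, so it could still continue under Section 4.3.4. Item 3 also applies to other laboratory values: a grade 4 value that has improved only to grade 2 by day 7 would clearly fall outside the exemption.
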